10. STUDY DESIGN

10.1 STUDY DESIGN

This is a retrospective, multi-center, case series study to collect clinical data that will evaluate post-market PEEK Anchors RAPTORMITE[®], DYNOMITE[®], SPYROMITE[®] and FOOTPRINT[®] ULTRA PK SL in extremities. A minimum of 80 subjects and a maximum of 480 subjects who underwent surgery for PEEK Anchors RAPTORMITE[®], DYNOMITE[®], SPYROMITE[®] and FOOTPRINT[®] ULTRA PK SL in extremities are planned to be enrolled into the study after the fulfilment of all inclusion and exclusion criteria. It is also planned that any of the investigational sites will enroll a minimum of 10 subjects into the study. Data from eligible subjects will be recorded on case report forms (CRFs).

10.2 STUDY ENDPOINTS

10.2.1 Primary Endpoint

Clinical success rate (%) of the study devices in extremities at 6 months post-operative with clinical success defined as extremity repairs without signs of device failure and/or re-intervention as assessed by the surgeon.

10.2.2 Secondary Endpoints

Clinical success rate (%) of the study devices in extremities at 12 months post-operative. Clinical success has previously been defined.

10.2.3 Safety Endpoints

Safety endpoints include the collection of the following events from the subjects' medical record:

CONFIDENTIAL AND PROPRIETARY

This document contains information that is confidential and proprietary to Smith & Nephew PLC and Smith & Nephew, Inc. and is intended for use only by Smith & Nephew and its manufacturer. It shall not be reproduced or copied in whole or in part, nor shall the contents be disclosed by any means without prior written permission from Smith & Nephew, nor shall anyone make any use of it that is contrary to the expressed or implied wishes of Smith & Nephew.

Study Protocol—Device	
Safety and Performance of PEEK Anchors (DYNOMITE [°] , SPYROMITE [°] , RAPTORMITE [°] , FOOTPRINT [°] ULTRA PK SL) in Extremities	Number: 2018.15.SMD.PEEK.RET.EXT
	Version: 2.0 05Dec2018
	Page: Page 26 of 54

- All adverse events (AEs) and complications occurring from the time of subject enrollment until study termination or study completion including intra-operative adverse events and complications.
- Device related re-intervention.
- Device deficiency.

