11. STUDY PROCEDURES

11.1 RETROSPECTIVE DATA COLLECTION: 6 MONTHS POST-OPERATIVE (±90 DAYS)

Given the retrospective study design, data will be collected from the medical chart to the extent it is available.

1. Subject should undergo the informed consent process and sign the informed consent *only* if a waiver of consent has not been approved by the IRB.
2. Screen the subject's chart for protocol inclusion/exclusion criteria.
3. Obtain demographic information and a medical history.
4. VAS, ROM.
5. Operative Data Collection – review operative case notes.

CONFIDENTIAL AND PROPRIETARY

This document contains information that is confidential and proprietary to Smith & Nephew PLC and Smith & Nephew, Inc. and is intended for use only by Smith & Nephew and its manufacturer. It shall not be reproduced or copied in whole or in part, nor shall the contents be disclosed by any means without prior written permission from Smith & Nephew, nor shall anyone make any use of it that is contrary to the expressed or implied wishes of Smith & Nephew.

Study Protocol—Device	
Safety and Performance of PEEK Anchors (DYNOMITE°, SPYROMITE°, RAPTORMITE°, FOOTPRINT° ULTRA PK SL) in Extremities	Number: 2018.15.SMD.PEEK.RET.EXT
	Version: 2.0 05Dec2018
	Page: Page 27 of 54

6. Implant Status/ Disposition.
7. Document concomitant medications and/or therapies associated with an AE, SA(D)E.
8. Review the subject’s chart for AEs, SAEs and Device Deficiencies, including inter-operative. AEs, SAEs and DevDs should be documented from the time of surgery through the study duration.

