14. ADVERSE EVENTS AND DEVICE DEFICIENCIES

Adverse Events (AE) related to the study implant, or procedure including Adverse Device Effects (ADE), Serious Adverse Device Effects (SADE), Unanticipated Serious Adverse Device Effect (USADE), and Device Deficiencies (DevD) occurring from the time of the surgery until revision or study completion must be recorded on the appropriate CRF and reported. If the event is known to have been previously reported to Smith & Nephew, this must be noted on the CRF. After enrollment, in addition to all adverse events related to the implant or the procedure, all serious adverse events (SAE), regardless of causality, must be recorded on the appropriate CRF and reported to the Sponsor, and IRB if necessary. Adverse events leading to a revision should be reported at all times regardless of causality.

Adverse Device Effects (ADE) occurring after study completion will be handled as product complaints reportable by the Sponsor and will not be entered into the study database.

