14.1.1 Adverse Event (AE)

An AE is any untoward medical occurrence temporally associated with the use of an Investigational Product (IP)/Ancillary Product, whether or not considered causally related to that IP/Ancillary Product.

AE is used both to refer to AEs which are non-serious non-IP or procedure-related and as an umbrella term referring to adverse events of all classifications.

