14.2 REPORTING PROCEDURES

AEs of any kind and DevDs will be recorded in the applicable CRF and source notes. The Investigator will evaluate all AEs for relationship to the device and procedure, if applicable, seriousness, and severity. ADEs, SAEs, and DevDs will be submitted/entered into the CRF and reported to the Sponsor within 24 hours of the Investigator being informed about the event (Figure 1). For ADEs and DevDs, details of the product/procedure related to the event will be recorded in the CRF within 24 hours of the retrospective chart review.

All SAEs and ADEs will be reviewed by a medically qualified person appointed by the Sponsor to determine which, if any, meet criteria for expedited reporting to the regulatory authorities. The Investigator will inform the IRB of AEs according to the IRB requirements.

Depending on the nature of the AE, the Sponsor may request copies of the subject’s medical records, imaging, operative notes, as well as results of any relevant laboratory tests performed or other documentation related to the AE. If the subject was hospitalized, a copy of the discharge summary may be requested by the Sponsor and should be forwarded as soon as it becomes

[figure not shown]
CONFIDENTIAL AND PROPRIETARY

This document contains information that is confidential and proprietary to Smith & Nephew PLC and Smith & Nephew, Inc. and is intended for use only by Smith & Nephew and its manufacturer. It shall not be reproduced or copied in whole or in part, nor shall the contents be disclosed by any means without prior written permission from Smith & Nephew, nor shall anyone make any use of it that is contrary to the expressed or implied wishes of Smith & Nephew.

Study Protocol—Device	
Safety and Performance of PEEK Anchors (DYNAMITE°, SPYROMITE°, RAPTORMITE°, FOOTPRINT° ULTRA PK SL) in Extremities	Number: 2018.15.SMD.PEEK.RET.EXT
	Version: 2.0 05Dec2018
	Page: Page 36 of 54

available. In certain cases, the Sponsor also may request a letter from the Investigator that summarizes the events related to the case.

Figure 1: Evaluation and Reporting of AE and DevD

Reference the Investigator Site File Sponsor Contact Information Sheet to report SAEs, unanticipated ADEs and SADEs, anticipated SADEs, and DevDs.

CONFIDENTIAL AND PROPRIETARY

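### Section 10.2.3 starts the adverse event endpoint at enrolment, at least three months after surgery, whereas 11.1 and 11.2 start it at surgery

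*Combined protocol and SAP*

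**What the plan says.** Section 10.2.3 lists all AEs and complications "occurring from the time of subject enrollment until study termination or study completion including intra-operative adverse events and complications". Its other two items, device-related re-intervention and device deficiency, carry no start date.

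The abstraction instructions in 11.1 read "AEs, SAEs and DevDs should be documented from the time of surgery through the study duration", and 11.2 repeats the sentence.

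The opening of section 14 has three rules:

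- Implant- or procedure-related AEs and device deficiencies "occurring from the time of the surgery until revision or study completion must be recorded on the appropriate CRF and reported".
- All-cause SAEs, introduced by "After enrollment, in addition to all adverse events related to the implant or the procedure, all serious adverse events (SAE), regardless of causality", must also be recorded on the CRF and reported.
- "Adverse events leading to a revision should be reported at all times regardless of causality".

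Section 14.1.1 defines an AE as "any untoward medical occurrence temporally associated with the use of an Investigational Product (IP)/Ancillary Product, whether or not considered causally related", and 14.2 says "AEs of any kind and DevDs will be recorded in the applicable CRF and source notes".

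Section 12.4 tabulates events that occur on-study and gives that term no start or end date. Section 12 says the SAP will be based on the protocol and finalised before database lock.

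**The concern.** An endpoint definition and the instructions for collecting its data should share one time origin. Here they do not, and the endpoint definition also conflicts with itself, because no intra-operative event can follow enrolment in this design.

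Safety over 6 months after intervention is part of the primary objective (7.1), and over 12 months part of the secondary objective (7.2). The 12.4 tables of overall AE incidence, SAEs and AEs by relatedness depend on which window sites and the SAP adopt. With up to 15 sites (synopsis), some could abstract from surgery and others from enrolment, and the pooled incidences would then mix two windows. The SAP can define on-study later, but it cannot restore events that a site never took from the chart.

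**Working it through.** The plan states no figure on this point, so there is none to reproduce. The check is a comparison of texts, followed by a bound on the literal reading.

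**Step 1: earliest enrolment.** Section 9.3 excludes subjects less than 3 months post-operative. Section 9.6 counts a subject as enrolled only after the criteria are met and consent or a waiver is in place. Section 9.5 rules out prospective visits. So enrolment falls at least 3 months after surgery for every eligible subject.

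**Step 2: start dates side by side.**

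| Section | Events | Start |
|---|---|---|
| 10.2.3 | all AEs and complications | enrolment, yet including intra-operative events |
| 11.1, 11.2 | AEs, SAEs, device deficiencies | surgery |
| 14, opening | related AEs, device deficiencies | surgery |
| 14, opening | all-cause SAEs | *After enrollment*: could date the event or the recording |
| 14, opening | AEs leading to revision | at all times |
| 12.4 | on-study events | not stated |

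**Step 3: size of the literal reading.** Let E be the enrolment day counted from surgery and W the day the period ends. The share of the period lost, intra-operative events apart, is min(E, W)/W. The schedule of events gives W = 182 and 365. Adding the 90-day allowance gives 182 + 90 = 272 and 365 + 90 = 455. The documents give no enrolment dates, so E is an assumption. Its minimum is 3 months, taken as 91 days.

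| E (assumed) | W = 182 | W = 272 | W = 365 | W = 455 |
|---|---|---|---|---|
| 91 (minimum) | 50.0% | 33.5% | 24.9% | 20.0% |
| 182 | 100% | 66.9% | 49.9% | 40.0% |
| 365 | 100% | 100% | 100% | 80.2% |

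Three calendar months run from 89 to 92 days. That moves the minimum only slightly: 89/182 = 48.9% to 92/182 = 50.5%, and 89/365 = 24.4% to 92/365 = 25.2%. With a surgery start, as in 11.1 and 11.2, the share lost is 0%.

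**Step 4: which events are exposed.** Related AEs and device deficiencies are required from surgery by the opening of section 14, and AEs leading to revision are required at all times. That leaves other unrelated AEs. It also leaves unrelated SAEs, if *After enrollment* is taken to date the event.

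**The case against.** The strongest reply is that the intent is plain. Section 5.2 names intra-operative safety, the objectives run from intervention, 10.2.3 itself mentions intra-operative events, and the abstraction instructions say surgery twice. A site following 11.1 and 11.2 loses nothing. This stands as a limit on the size of the problem. It does not remove the error, because no section gives 11.1 and 11.2 precedence over the endpoint definition on which the SAP will draw.

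A reader might infer three stronger points that the documents do not support:

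- *Section 14 leaves out unrelated non-serious AEs.* Its opening does not call for them unless they lead to revision, but it excludes nothing. Section 14.2 belongs to the same section and records AEs of every kind. The schedule of events has a separate AE assessment row, and 14.3.1 provides for following unrelated AEs. The opening and 14.2 need aligning, but the protocol as a whole points to all AEs.
- *All-cause SAEs start at enrolment.* The phrase can equally mean that the duty to record begins once the subject is enrolled, and 11.1 and 11.2 start SAEs at surgery. This calls for clarification and is not a demonstrated second error.
- *The end dates conflict throughout.* Study completion and study duration are near-synonyms in a chart review with twelve months of follow-up. Only the *until revision* limit in section 14 differs in substance.

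**Conclusion.** The start of the AE endpoint in 10.2.3 is wrong as written and should be corrected. On the literal reading, at least about half of the nominal 6-month period and a quarter of the 12-month period fall outside the window. Measured to the outer edge of the visit allowances, the minimum is about a third and a fifth. These are shares of follow-up time, not of events. No effect on event rates can be estimated, because the documents give neither AE rates nor enrolment dates.

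A reader might infer that the study will lose half of its 6-month safety data. The documents do not support that. The loss arises only where 10.2.3 is followed in preference to 11.1 and 11.2, and it then falls mainly on unrelated AEs and possibly unrelated SAEs. Clinical success, the primary endpoint, is not affected.

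**What to change.** Three changes settle the start date:

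1. In 10.2.3, replace the enrolment start with the time of surgery.
2. In the opening of section 14, make clear that *After enrollment* refers to when SAEs are recorded, and that all-cause SAEs dated from surgery onwards are included.
3. In 12.4, define on-study with the same surgery start.

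Two secondary clarifications belong in the same amendment. Reconcile the scope in the opening of section 14 (related AEs, all-cause SAEs, AEs leading to revision) with 14.2. Reconcile the *until revision* limit in section 14 with the end wording in 10.2.3, 11.1 and 11.2; the end date is for the sponsor to set.

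The cost is a few wording changes, plus slightly more chart abstraction at any site that would have applied the narrower rule. The changes should be in place before sites abstract charts.

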10.2.4 Other Endpoints

Surgeon Reported Outcomes would constitute other endpoints and may include but not be restricted to the following:

- Range of Motion (ROM)
- Pain assessed by Visual Analogue Scale (VAS)

Surgeon reported outcomes are optional and will be definitively specified in collaboration with the Investigators once sites have been identified for the conduct of the study.

11. STUDY PROCEDURES

11.1 RETROSPECTIVE DATA COLLECTION: 6 MONTHS POST-OPERATIVE (±90 DAYS)

Given the retrospective study design, data will be collected from the medical chart to the extent it is available.

1. Subject should undergo the informed consent process and sign the informed consent *only* if a waiver of consent has not been approved by the IRB.
2. Screen the subject's chart for protocol inclusion/exclusion criteria.
3. Obtain demographic information and a medical history.
4. VAS, ROM.
5. Operative Data Collection – review operative case notes.

CONFIDENTIAL AND PROPRIETARY

This document contains information that is confidential and proprietary to Smith & Nephew PLC and Smith & Nephew, Inc. and is intended for use only by Smith & Nephew and its manufacturer. It shall not be reproduced or copied in whole or in part, nor shall the contents be disclosed by any means without prior written permission from Smith & Nephew, nor shall anyone make any use of it that is contrary to the expressed or implied wishes of Smith & Nephew.

Study Protocol—Device	
Safety and Performance of PEEK Anchors (DYNOMITE°, SPYROMITE°, RAPTORMITE°, FOOTPRINT° ULTRA PK SL) in Extremities	Number: 2018.15.SMD.PEEK.RET.EXT
	Version: 2.0 05Dec2018
	Page: Page 27 of 54

6. Implant Status/ Disposition.
7. Document concomitant medications and/or therapies associated with an AE, SA(D)E.
8. Review the subject’s chart for AEs, SAEs and Device Deficiencies, including inter-operative. AEs, SAEs and DevDs should be documented from the time of surgery through the study duration.

11.2 RETROSPECTIVE: 12 MONTHS POST-OPERATIVE (±90 DAYS)

Given the retrospective study design, data will be collected from the medical chart to the extent it is available.

1. VAS, ROM.
2. Implant Status/Disposition.
3. Document concomitant medications and/or therapies associated with an AE, SA(D)E.
4. Review the subject’s chart for AEs, SAEs and Device Deficiencies including inter-operative. AEs, SAEs and DevDs should be documented from the time of surgery through the study duration.
5. Complete the End of Study CRF.

11.3 CONCOMITANT MEDICATIONS AND THERAPIES

Any concomitant medications associated with an AE, SAE or SADE will be recorded.

12. STATISTICAL DESIGN

A Statistical Analysis Plan (SAP) based on the contents of the protocol will be written and finalized prior to database lock. The SAP will account for any changes or deviations from the projected analyses in this protocol.

CONFIDENTIAL AND PROPRIETARY

This document contains information that is confidential and proprietary to Smith & Nephew PLC and Smith & Nephew, Inc. and is intended for use only by Smith & Nephew and its manufacturer. It shall not be reproduced or copied in whole or in part, nor shall the contents be disclosed by any means without prior written permission from Smith & Nephew, nor shall anyone make any use of it that is contrary to the expressed or implied wishes of Smith & Nephew.

Study Protocol—Device	
Safety and Performance of PEEK Anchors (DYNOMITE [°] , SPYROMITE [°] , RAPTORMITE [°] , FOOTPRINT [°] ULTRA PK SL) in Extremities	Number: 2018.15.SMD.PEEK.RET.EXT
	Version: 2.0 05Dec2018
	Page: Page 28 of 54

12.1 GENERAL

Smith & Nephew’s Global Biostatistics group will conduct the statistical analysis for this study. Unless otherwise stated, all significance tests will be two-sided, performed at the 5% significance level. Resulting p-values will be quoted and 95% two-sided confidence intervals will be generated where appropriate.

Where data summaries are specified, categorical and ordinal variables will be summarized with frequencies and percentages. Continuous variables will be summarized with the following summary statistics: number of observations, mean, median, standard deviation, minimum and maximum values. All analyses will be performed in Statistical Analysis System (SAS) version 9.3 (or later).

12.2 ANALYSIS POPULATIONS

The following analysis populations will be used for this study:

- **Safety Population (SAF):** This includes all subjects who enroll in the study who had previously undergone repair in the extremities using any of the PEEK anchors: RAPTORMITE[°], DYNOMITE[°], SPYROMITE and FOOTPRINT[°] ULTRA PK SL.
- **Per-Protocol Population (PP):** This includes all subjects in the Safety Population, who have no significant protocol deviations and who meet all the inclusion/exclusion criteria. Deviations considered as significant will be defined and finalized prior to database lock.

12.3 EFFICACY ANALYSIS

Analysis of Primary Endpoint

CONFIDENTIAL AND PROPRIETARY

This document contains information that is confidential and proprietary to Smith & Nephew PLC and Smith & Nephew, Inc. and is intended for use only by Smith & Nephew and its manufacturer. It shall not be reproduced or copied in whole or in part, nor shall the contents be disclosed by any means without prior written permission from Smith & Nephew, nor shall anyone make any use of it that is contrary to the expressed or implied wishes of Smith & Nephew.

Study Protocol—Device	
Safety and Performance of PEEK Anchors (DYNOMITE°, SPYROMITE°, RAPTORMITE°, FOOTPRINT° ULTRA PK SL) in Extremities	Number: 2018.15.SMD.PEEK.RET.EXT
	Version: 2.0 05Dec2018
	Page: Page 29 of 54

The rate (%) of clinical success of all the anchor devices combined at 6 months post-operative will be summarized as a frequency and a percentage. A 95% two-sided exact CI for a single proportion will be presented using Clopper-Pearson’s method (1934). The same type of analysis will be carried out for each of the anchors used in the study. These analyses will be carried out using the per protocol population as the primary analysis population with the safety population used for sensitivity analysis.

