9.3 EXCLUSION CRITERIA

Any one (1) of the following criteria will disqualify a potential subject from participation in the study:

1. Subject is entered in another investigational drug, biologic, or device study or has been treated with an investigational product within 12 months post-operative.
2. Subjects who are < 3 months post-operative.

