9.5 INFORMED CONSENT

Study sites will obtain Institutional Review Board (IRB/Ethics Committee (EC)) approval for this study before any study specific activities are performed.

Due to the retrospective nature of the study, a waiver of informed consent for study participation will be requested from the IRB/EC for those subjects who meet eligibility criteria as only retrospective data set will be collected for these subjects. No prospective visits will be performed.

A waiver or alteration of the requirements for obtaining informed consent can occur under any of the following three provisions set forth by the Department of Health and Human Health Services:

Research in general: an IRB may waive or alter the requirement of informed consent under 45 CFR 46.116(d), provided that the IRB finds and documents that all of the following four conditions are met:

CONFIDENTIAL AND PROPRIETARY

This document contains information that is confidential and proprietary to Smith & Nephew PLC and Smith & Nephew, Inc. and is intended for use only by Smith & Nephew and its manufacturer. It shall not be reproduced or copied in whole or in part, nor shall the contents be disclosed by any means without prior written permission from Smith & Nephew, nor shall anyone make any use of it that is contrary to the expressed or implied wishes of Smith & Nephew.

Study Protocol—Device	
Safety and Performance of PEEK Anchors (DYNOMITE [®] , SPYROMITE [®] , RAPTORMITE [®] , FOOTPRINT [®] ULTRA PK SL) in Extremities	Number: 2018.15.SMD.PEEK.RET.EXT
	Version: 2.0 05Dec2018
	Page: Page 23 of 54

1. the research involves no more than minimal risk to the participants;
2. the waiver or alteration will not adversely affect the rights and welfare of the participants;
3. the research could not practicably be carried out without the waiver or alteration; and
4. Whenever appropriate, the participants will be provided with additional pertinent information after participation.

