9.6 ENROLLMENT

For screening, only information available in the medical records will be reviewed. Once a potential subject has been identified, all inclusion criteria and none of the exclusion criteria have been met, and the informed consent process has been completed or a waiver of consent has been granted by IRB/EC, the subject will be considered enrolled and assigned a consecutive Subject

CONFIDENTIAL AND PROPRIETARY

This document contains information that is confidential and proprietary to Smith & Nephew PLC and Smith & Nephew, Inc. and is intended for use only by Smith & Nephew and its manufacturer. It shall not be reproduced or copied in whole or in part, nor shall the contents be disclosed by any means without prior written permission from Smith & Nephew, nor shall anyone make any use of it that is contrary to the expressed or implied wishes of Smith & Nephew.

Study Protocol—Device	
Safety and Performance of PEEK Anchors (DYNOMITE°, SPYROMITE°, RAPTORMITE°, FOOTPRINT° ULTRA PK SL) in Extremities	Number: 2018.15.SMD.PEEK.RET.EXT
	Version: 2.0 05Dec2018
	Page: Page 24 of 54

Identification (ID) number. Enrollment and assigned Subject ID will be documented on the Screening and Enrollment Log. For bilateral subjects, only one Subject ID will be assigned.

Any subject who signs an informed consent or has a waiver of informed consent and is subsequently identified as not meeting the required entry criteria is considered to be a screen failure. Demographic information must be captured in the appropriate Case Report Form (CRF) and the reason for screen failure will be documented on the Screening and Enrollment Log.

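### The headline 6-month success rate rests on a per-protocol set whose excluding deviations may be defined as late as database lock, when most outcomes are already in the charts

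*Combined protocol and SAP*

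**What the plan says.** Section 12.3 sets out the primary analysis, the 6-month success rate with an exact Clopper-Pearson interval, for all anchors combined and for each anchor. On the analysis set it says: "These analyses will be carried out using the per protocol population as the primary analysis population with the safety population used for sensitivity analysis".

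Section 12.2 defines the safety population as all enrolled subjects repaired with a study anchor. The per-protocol population is the part of it that meets all entry criteria and has no significant deviation. No deviation is listed. Instead: "Deviations considered as significant will be defined and finalized prior to database lock". Section 12 gives the SAP the same deadline; it "will be written and finalized prior to database lock".

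Four other places bear on this:
- Section 9.6: a subject with consent or a waiver who is "subsequently identified as not meeting the required entry criteria is considered to be a screen failure".
- Section 9.5: "No prospective visits will be performed". Section 11.1 takes data from the chart as far as they exist.
- Section 9.3 excludes "Subjects who are < 3 months post-operative".
- Section 10.2.1 defines success as a repair "without signs of device failure and/or re-intervention as assessed by the surgeon".

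For the 12-month rate, with the same definition of success, section 12.3.2 uses the safety population.

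**The concern.** In a prospective study, fixing deviations before lock gives some protection, especially if those who decide have not seen outcomes. Here that protection is weak. The outcome has usually happened, and been written down, before the chart is opened. The surgeon judges success, and the protocol describes no masking of those who define or classify deviations. The rule that decides who counts in the headline rate can therefore be written, and applied case by case, when outcomes are known or easy to look up.

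At stake is the estimate that carries the primary label. If exclusions are related to outcome, that estimate shifts. If they are not, it does not shift systematically. The 6- and 12-month headline rates would also rest on different sets although they share one definition of success.

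**Working it through.** **Inputs.** Assumed success rate 91%, 20 to 120 subjects per anchor and 80 to 480 overall (section 13). Clopper-Pearson 95% limits (section 12.3). 6-month window of 182 ± 90 days (Table 1). The documents give no number of per-protocol exclusions, so one is assumed, with two as a wider case. Success counts are the whole numbers nearest 91%: 18/20, 73/80, 109/120, 437/480.

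**The plan's own figure.** Section 13 gives a probability of 15.2% to above 95% of reaching the target precision. The protocol does not state the criterion. Reading it as an exact interval with half-width of at most 91 − 80 = 11 points, only 20/20 qualifies at n=20, so the probability is 0.91^20 = 0.1516. At n=120 it is 1.000. Both ends agree with the plan. The point below does not depend on this figure.

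**Timing.** The window opens at day 182 − 90 = 92, about the minimum time since surgery for entry. Section 9.1 enrolls from the earliest surgery forward. Most 6-month outcomes should therefore be charted before lock. This holds for most subjects, not all: one entered just past 3 months may have later follow-up still to come.

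**What separates the two sets.** Per-protocol is the safety set minus subjects with significant deviations and minus ineligible subjects. Section 9.6 already turns later-found ineligible subjects into screen failures. The unlisted deviations are therefore likely to be the main difference.

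**Size.** With x successes in n:
- excluding one failure changes the rate by x/(n−1) − x/n = x/[n(n−1)];
- excluding one success changes it by (x−1)/(n−1) − x/n = −(n−x)/[n(n−1)].

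At n=20, x=18 these are 18/380 = +4.7 points and −2/380 = −0.5 points.

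| Safety set (95% CI) | One failure excluded (95% CI) | Shift, points |
|---|---|---|
| 18/20 = 90.0% (68.3–98.8) | 18/19 = 94.7% (74.0–99.9) | +4.7 |
| 109/120 = 90.8% (84.2–95.3) | 109/119 = 91.6% (85.1–95.9) | +0.8 |
| 73/80 = 91.3% (82.8–96.4) | 73/79 = 92.4% (84.2–97.2) | +1.2 |
| 437/480 = 91.0% (88.1–93.4) | 437/479 = 91.2% (88.3–93.6) | +0.2 |

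Excluding one success at n=20 gives 17/19 = 89.5% (66.9–98.7).

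Wider case, two failures excluded: 18/18 = 100% (81.5–100) at n=20, +10.0 points; 73/78 = 93.6% at n=80, +2.3; 437/478 = 91.4% at n=480, +0.4.

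If the single exclusion at n=20 is random, it is a failure with probability 2/20 = 0.10. The expected rate is 0.10 × 18/19 + 0.90 × 17/19 = 0.900, so there is no shift on average.

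**The case against.** The strongest reply is that the plan already contains the remedy. The safety-set analysis of the same rates is committed to, pooled and per anchor. Per-protocol is a subset of the safety set, so the effect of any exclusion shows as a gap between two planned estimates. This stands, and it limits the concern to which figure is labelled primary. The comparison is clean only if missing 6-month outcomes are treated alike in both sets; that is a separate matter.

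Second, the mechanism is not shown. An outcome in a site's chart is not necessarily known to whoever classifies deviations. Section 12.1 gives the analysis to the sponsor's biostatistics group, and no section says who classifies. With no study visits and surgery under local standard of care, there may be few deviations at all. This also stands.

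Third, per-protocol can be a defensible choice for a device. Table 4 marks some anchor and indication pairs as not applicable, section 8.6 describes use according to the labelling, and section 9.2 does not require on-indication use. If off-indication use were listed as significant, per-protocol would describe performance as labelled. The documents do not say that it will be. If it is the intention, it can be listed before abstraction.

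Two stronger readings are tempting. A reader might infer that the plan inflates the success rate. The documents do not support that: they name no deviation that would remove failures, and exclusions unrelated to outcome produce no systematic shift. A reader might also infer that the undefined deviations are all that separates the two sets. Section 12.2 has its own eligibility clause, and no section says that a screen failure identified after enrollment leaves the safety set.

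**Conclusion.** The point holds as an avoidable bias risk to the headline rate. A deadline of database lock does not ensure, in a chart review, that membership of the primary set is settled without knowledge of outcome. Confidence is moderate, because the documents show an opportunity and not an occurrence.

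The consequence is bounded. Section 13 makes the study precision-based, with no powered test and no stated pass or fail threshold, so what changes is the reported estimate and its interval. Per anchor the concern is material near n=20 and small at n=120. For the pooled rate it is small. All shifts rest on assumed exclusion counts and on success near 91%; the table shows the unfavourable case, in which the excluded subject is a failure.

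**What to change.** In section 12.3, make the safety population primary for the 6-month rate, pooled and per anchor, with per-protocol as the sensitivity analysis. This matches section 12.3.2.

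In section 12.2:
- fix the list of significant deviations before chart abstraction starts, in place of the database-lock deadline;
- bar any deviation that depends on outcome;
- classify deviations from a listing that omits implant status, device failure and re-intervention;
- report per-protocol exclusions by reason and by success status.

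The cost is two labels exchanged, one list brought forward, one masked listing and one table. The downside is that the primary rate may be slightly lower. It may also include ineligible subjects not already made screen failures, or off-indication cases if those would have been listed as significant. The per-protocol sensitivity analysis would still show the rate without them.
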